3.2 Allocation to Treatment Groups and Blinding

Randomization: A blocked randomization scheme (with block sizes that vary randomly between 2 and 4) will be employed to initially randomize subjects to NCS or placebo at baseline; the same approach will then be employed for the re-randomization at 3 months, when the subjects who were initially randomized to receive NCS will be re-randomized in equal numbers to receive NCS or placebo. The randomization will be stratified according to atopy/asthma, current use of inhaled corticosteroids for asthma (yes/no), obesity status and seasonality (spring/summer vs autumn/winter). Programs will be written in Stata to conduct the randomization, and the assignments will be stored in sealed envelopes stored in a locked cabinet that is only accessible to CTSA staff who are not affiliated with other aspects of the

study.

Blinding: The study will be double-blinded. All subjects, their families, investigators and study team members will be blinded, except for one research coordinator. In order to avoid bias and equipoise shifting, two research coordinators will be part of this study. One of them will be responsible for enrolling subjects and will be blinded to the treatment allocation status. The other research coordinator will be responsible for breaking the blind at the 3 month visit. She will refer participants allocated to placebo to clinical care, and communicate with the statistician regarding the randomization of participants initially allocated to NCS. Other investigators will evaluate research data (e.g., read polysomnograms) that are deidentified and coded to prevent becoming unblinded. Note that there is no physical exam after the baseline study. The statistician will generate a list of random numbers for study arm assignment, and a CTSA staff member who is not otherwise involved in the study will provide the drug/placebo.

3.3 Study Duration, Enrollment and Number of Sites

3.3.1 Duration of Study Participation

The study duration per subject will be up to 15 months total including 12 months since randomization. The extra days are to account for interpretation of the sleep study and scheduling of subjects, including potential cancellations due to family circumstances. Of note, subjects initially randomized to placebo will be in the study for 3 months following randomization.

3.3.2 Total Number of Study Sites/Total Number of Subjects Projected

The study will be conducted only at CHOP. It is expected that 318 children will be recruited to produce 159 evaluable subjects 3 months after randomization, and 100 at 12 months.

3.4 Study Population

3.4.1 Inclusion Criteria

- 1) Age 5-12 years of age.
- 2) Mild to moderate OSAS, defined as an obstructive apnea index (AI) of 1-20/hr of total sleep time (TST) or obstructive hypopnea apnea index (AHI) 2-30/hr of total sleep time (TST).
- 3) Parent-related symptoms of habitual snoring (>3 nights per week)
- 4) No history of adenotonsillectomy or prior NCS use.
- 5) Parental/guardian permission (informed consent) and if appropriate, child assent.

3.4.2 Exclusion Criteria

- 1) Severe OSAS or significant hypoxemia or hypercapnia on PSG, such that definitive treatment should not be delayed (AHI > 30/hr, more than 2% total sleep time with SpO₂ <90%, end-tidal PCO₂ > 60 mm Hg for > 5 minutes, pathologic arrhythmias)(4).
- 2) History of recurrent throat infections (as defined by the American Academy of Otolaryngology-Head and Neck Surgery Clinical Practice Guidelines For Tonsillectomy (7)) in the past few years as follows: > 7 episodes in the past year or > 5 episodes/year over the past 2 years or > 3 episodes/year over the past 3 years.
- 3) Abnormalities on baseline safety screening tests, i.e., DXA scan showing spine or whole body bone mineral density < -2.0 standard deviations using race specific curves with adjustment for height Z-score; (subjects may be randomized in the absence of DXA results; once the DXA results become available, subjects with abnormal results will be withdrawn from the study and referred for clinical care) or ophthalmologic exam demonstrating cataracts (except those with < 2 mm anterior polar cataracts), aphakia or other ocular abnormalities such as glaucoma, retinal coloboma, intraocular inflammation or microphthalmia.
- 4) Failure to thrive (weight/height < 5th percentile for age and gender), as this may be secondary to OSAS.
- 5) Severe obesity (BMI z-score > 3) as OSAS is likely to persist in these subjects.
- 6) Previous adenoidectomy unless adenoidal tissue has been documented to have regrown.
- 7) Previous adenotonsillectomy.
- 8) CPAP therapy.
- 9) Any NCS use in the past 3 months or NCS use for > 2 weeks in the past year.
- 10) Current immunotherapy or daily antihistamine use.
- 11) Recent (past month) nasal septum ulcers, surgery or trauma.
- 12) Other major illness other than asthma, such as craniofacial anomalies, endocrine or neuromuscular disease, or past history of cancer. This includes children with conditions that may be worsened by OSAS, such as hypertension or diabetes.
- 13) Current use of ketoconazole or other potent CYP3A4 inhibitors.
- 14) Families planning to move out of the area within the year.
- 15) Parents/guardians or subjects who, in the opinion of the Investigator, may be non-compliant with study schedules or procedures.
- 16) Pregnancy.

Subjects that do not meet all of the enrollment criteria may not be enrolled. Any violations of these criteria must be reported in accordance with IRB Policies and Procedures. Note that DXA results may not be available on the same day, in which case the participant will be randomized, but will later be withdrawn from the study and referred for clinical care if the DXA results are abnormal.

4 STUDY PROCEDURES

4.1 Screening Visit

- Informed Consent
- Medical Record Review
- Sleep study. Of note, participants who have undergone a recent sleep study (past 3 months) will not require a new one.

4.2 Study Treatment Phase

4.2.1 Visit 1: Baseline & Randomization

- History and Physical Exam
- Vital Signs
- Cognitive and behavioral measures
- Knee height measurement,
- DXA scan (immediately preceded by pregnancy test when indicated)
- Phlebotomy (biomarkers, genetics, and cortisol levels)
- Nasal swab (biomarkers, genetics)
- Ophthalmology evaluation
- OSAS symptoms questionnaires
- Nasal symptoms questionnaires
- Quality of life questionnaires
- Airway size measurement
- Spirometry

- Percutaneous skin allergy test
- Randomization
- Dispensation of NCS or placebo

4.3 Phase 2 of the Study

Participants randomized to both groups will receive monthly phone calls, keep an infection log, and come back at 3 months for a visit.

4.3.1 Visit 2

Detailed description of study visit including all procedures – listed like above examples.

- Sleep study
- Vital Signs
- Cognitive and behavioral measures
- Knee height measurement,
- DXA scan (immediately preceded by pregnancy test when indicated)
- Phlebotomy (biomarkers, genetics, and cortisol levels)
- Nasal swab (biomarkers, genetics)
- Ophthalmology evaluation
- OSAS symptoms questionnaires
- Nasal symptoms questionnaires
- Quality of life questionnaires
- Airway size measurement
- Weigh medication canister
- Participants in placebo group will end their participation in the study at the end of visit 2. They will be referred to clinical care
- Re-randomization of participants in NCS group
- Dispensation of NCS or placebo

4.4 Follow-up Phase (only if applicable)

Children in the NCS group who did not require referral to clinical care as detailed in 3.1.2 will be further randomized to either placebo or continuation of NCS. Half of the initial NCS group will continue treatment with NCS, and the other half will be switched to placebo. Participants re-randomized to both groups will receive monthly phone calls, keep an infection log

4.4.1 Visits 3 & 4

Will be scheduled at 3 and 6 months respectively after second randomization to help with retention.

- Interim medical history
- Vital Signs
- Weigh medication canister
- OSAS symptoms questionnaires and nasal symptoms questionnaire

4.4.2 Visit 5: End of Study

Detailed description of study visit including all procedures – listed like above examples.

- Sleep study
- Physical Exam
- Cognitive and behavioral measures
- Vital Signs
- Laboratory tests
- Knee height measurement,
- DXA scan (immediately preceded by pregnancy test when indicated), blood work (biomarkers, genetics, and cortisol levels), ophthalmology evaluation,
- OSAS symptoms questionnaires
- Nasal symptoms questionnaires
- Quality of life questionnaires
- Airway size measurement
- Weigh medication canister

- Participants in both groups with persistent polysomnographic abnormalities are referred to clinical care.

4.5 Unscheduled Visits

In the rare circumstance where a patient requires an unscheduled visit for a true emergency, they will be seen in the Emergency Department. For minor issues, they will be seen by a member of the investigative team in a clinically appropriate time frame.

4.6 Concomitant Medication

All prior and concomitant medications used within 3 months prior to the screening visit and through the end of the study will be recorded. The dates of administration, dosage, and reason for use will be included.

4.7 Rescue Medication Administration

N/A

4.8 Subject Completion/Withdrawal

Subjects may withdraw from the study at any time without prejudice to their care. They may also be discontinued from the study at the discretion of the Investigator for lack of adherence to study treatment or visit schedules, or AEs. The Investigator may also withdraw subjects who violate the study plan, or to protect the subject for reasons of safety or for administrative reasons. It will be documented whether or not each subject completes the clinical study. If the Investigator becomes aware of any serious, related adverse events after the subject completes or withdraws from the study, they will be recorded in the source documents and on the CRF.

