Statistical And Analytic Plan	
 • It is assumed that 50% of subjects will fail the baseline screening PSG. Thus, 318 subjects will be recruited initially. • 159 eligible subjects will be randomized in a 2:1 fashion to NCS vs. placebo, respectively; the initial group sizes will therefore be 106 NCS vs. 53 placebo subjects. The 2:1 randomization ratio is to allow for further randomization during the follow-up phase of the study. Based on our past studies we will assume a drop-out rate of 5% at 3 months. Therefore, the available sample size for analysis for Aim 1 will be 100 NCS vs. 50 placebo subjects. • All analyses will be conducted with Stata 13.0, with two-sided tests of hypotheses and a p-value < 0.05 as the criterion for statistical significance. • Analyses will be conducted according to the intent to treat principle, with subjects analyzed according to their initial treatment assignment. • Descriptive analyses will include computation of means (with 95% confidence intervals), standard deviations, medians, interquartile-ranges (IQR) of continuous variables and tabulation of categorical variables. • A two-group t-test for independent samples or Wilcoxon rank sum test will be used to test the primary hypothesis that

the changes in AHI are equal between the two treatment groups.

[figure not shown]
DATA AND SAFETY MONITORING PLAN

Participants' data will be closely monitored by an external Data Safety Monitoring Board (DSMB) and an external safety officer. They will monitor adverse events and treatment failures.

TABLE 1: SCHEDULE OF STUDY PROCEDURES

Percutaneous skin allergy test		X												
Blood tests		X			X									X
Ophthalmology exam		X			X									X
Nasal secretion testing		X			X									X
DXA scan		X			X									X
Urine pregnancy test		X			X									X
Randomization		X			X									
Dispense Study Drug		X			X									
Drug Compliance					X		X				X			X
Adverse Event Assessment		X	X	X	X	X	X	X	X	X	X	X	X	X

FIGURE 1: STUDY DIAGRAM

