4.8.1 Early Termination Study Visit

Subjects who withdraw from the study will have all procedures enumerated for Visit 5 at the early termination visit.

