6.3.2 Efficacy Analysis

The primary analysis will be based on an intention to treat approach and will include all subjects randomized at Visit 1.

The primary efficacy endpoint will be the change in AHI between Randomization and Visit 2.

Secondary endpoints will include the change in AHI at the 12-month visit in each group and the change in knee height, bone health, adrenal suppression, ocular health and infection at 12 months.

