8.11 Regulatory and Ethical Considerations

8.11.1 Data and Safety Monitoring Plan

- The study will have an external Data Safety Monitoring Board (DSMB) and an external unblinded medical monitor.
- The role of the medical monitor will be similar to that used in the Childhood Adenotonsillectomy Trial (CHAT) trial.(4) The Medical Monitor ([name], Johns Hopkins University) is a pediatric pulmonologist and sleep specialist. She will have access to unblinded data should the need arise for a “real time,” clinically urgent decision regarding a subject’s continued study participation. A class of outcomes will be established denoted as “Treatment Failures.” This will be defined as a change in clinical status interpreted by the safety officer as requiring an immediate change to established clinical therapy for OSAS. Operationally, treatment failures will be identified by the research coordinator based on interim telephone calls and research visits, or contacts initiated by the subject. Information will be submitted to the safety officer who will make a final adjudication of the status of the subject. Data will be subsequently reviewed by the DSMB. The P.I. will make the final determination regarding withdrawing individual subjects. Note that as the study will utilize an intent to treat paradigm, every effort will be made to continue the subject in the study, regardless of whether the subject receives clinical treatment or not. Examples of treatment failures include worsening symptoms of OSAS such as sleepiness interfering with schoolwork, or development of complications associated with OSAS such as failure to thrive. Note that in the CHAT study there were only 9 of 464 (1.9%) children designated as treatment failures, so the numbers in the current study are expected to be low.
- The DSMB will be responsible for overall participants’ safety during the study. The DSMB will be comprised of a pediatric pulmonologist, [name] [name]; a neonatologist and sleep medicine expert, [name]; a pediatric otolaryngologist, [name]; and a biostatistician, [name].
- DSMB members are experts in their field and are unrelated to this research.
- DSMB members do not have active or pending scientific collaborations with study investigators
- The DSMB will meet twice a year. The meetings will be held via teleconference.
- Once a month, the Medical Monitor and DSMB will receive reports of all adverse events

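### Section 4.8 lets the investigator take randomized children out of the study for non-adherence or plan violations, which conflicts with the intention-to-treat analysis of all randomized children and can bias the comparison in either direction

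*Combined protocol and SAP*

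**What the plan says.** Section 4.8 (Subject Completion/Withdrawal) says children may be "discontinued from the study at the discretion of the Investigator for lack of adherence to study treatment or visit schedules". It adds: "The Investigator may also withdraw subjects who violate the study plan", and it also permits withdrawal for safety or administrative reasons. In each case the child leaves the study; the text does not separate stopping study drug from stopping assessment.

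Section 6.3.2 (Efficacy Analysis) says: "The primary analysis will be based on an intention to treat approach and will include all subjects randomized at Visit 1". The synopsis agrees: "Analyses will be conducted according to the intent to treat principle, with subjects analyzed according to their initial treatment assignment". The endpoint is tied to a visit: "The primary efficacy endpoint will be the change in AHI between Randomization and Visit 2".

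Section 4.8.1 provides one further assessment: "Subjects who withdraw from the study will have all procedures enumerated for Visit 5 at the early termination visit". Visit 5 includes a sleep study (section 4.4.2).

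Section 8.11.1, writing about treatment failures and giving the intent-to-treat approach as its reason, says that "every effort will be made to continue the subject in the study, regardless of whether the subject receives clinical treatment or not".

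**The concern.** Whether a child uses the spray or keeps appointments becomes known only after randomization. It may depend on the assigned treatment or on how the child is doing, for example through nasal irritation, lack of benefit or worsening symptoms. If such children leave the study and their outcome is not collected, the children left in each arm are no longer the groups that randomization formed.

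The plan already screens for expected non-compliance before randomization (exclusion criterion 15 in section 3.4.2), where it does no harm to the comparison. Section 4.8 applies a similar filter afterwards, where it can. At stake are the 3-month primary comparison and, more so, the 12-month comparison of continued NCS with the switch to placebo.

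**Working it through.** **1. The passages side by side.** Section 6.3.2 needs an AHI at Visit 2 for every child randomized. Section 4.8 allows a child to be out of the study before Visit 2. Section 4.8.1 does not close the gap, for three reasons:
- it refers to subjects who withdraw, and does not say whether this includes children discontinued by the investigator;
- its sleep study takes place whenever the child leaves, not at month 3;
- nothing says whether that AHI enters any analysis.

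No method for missing AHI is given.

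**2. The plan's own figures.** Section 6.4 randomizes 106 to NCS and 53 to placebo and assumes 5% dropout at 3 months: 106 × 0.95 = 100.7 and 53 × 0.95 = 50.4, stated as 100 and 50. The primary analysis is therefore sized on the children who remain. For an effect size of 0.50 with a two-sided 0.05 t-test, the noncentrality is 0.50 × √(100 × 50 / 150) = 2.89 on 148 df. This gives 81.8% power (82.3% by the normal approximation), against 81% stated. The figure reproduces.

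**3. When could non-adherence be known?** Sections 7.1.4 and 7.2.4 measure compliance by canister weight at visits.
- *3-month endpoint.* Weighing is first listed at Visit 2 (sections 3.1.3 and 4.3.1), the same visit as the primary sleep study. Before then there are monthly phone calls and the family's record of keeping appointments.
- *12-month endpoint.* Canisters are weighed at months 6 and 9 (section 3.1.4), before the month-12 sleep study. Section 6.4 expects 50 × 0.90 = 45 children per arm.

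**4. Size at 3 months (illustration).** The documents give no rate of non-adherence. Assume a share q of NCS children is non-adherent and gets no benefit, all of them are removed, and adherent children gain 4.2/hr (the section 6.4 figure for an effect size of 0.50 at an SD of 8.4).
- Effect in all randomized: 4.2 × (1 − q). At q = 5%: 4.2 × 0.95 = 3.99, or 4.0/hr.
- Effect after removal: 4.2/hr.
- Overstatement: 1 / (1 − q) − 1 = 1 / 0.95 − 1 = 5.3%.

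Larger q would exceed the plan's own 5% dropout from all causes at 3 months, so it is not used.

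**5. Direction (illustration).** Suppose the drug does nothing and removed children have an AHI change g SD worse than their arm's mean. The false difference in favour of NCS is g × [qN / (1 − qN) − qP / (1 − qP)], where qN and qP are the shares removed from the NCS and placebo arms.
- Equal removal: zero.
- qN = 5%, qP = 0, g = 0.5 to 1: 0.5 × 0.05 / 0.95 = 0.026 SD, to 1 × 0.05 / 0.95 = 0.053 SD. That is 0.22 to 0.44/hr at SD 8.4, or 0.05 to 0.11/hr at SD 2.
- qN = 0, qP = 5%: the same amounts against NCS.

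The values of g are assumptions.

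**The case against.** The strongest reply is that section 4.8 is a discretionary permission, not a rule to remove every non-adherent child. Children who stay are analysed as assigned. Investigators are blinded (sections 3.2 and 8.8.2), which makes removal driven by arm less likely. Non-adherence measured by canister can hardly remove a child before the primary sleep study, and a child who misses visits may have no month-3 sleep study whatever section 4.8 says. All of this stands, and it limits the size of the problem at 3 months. It does not remove the conflict: blinding does not prevent selection of adherers, and missed visits are themselves a stated ground for discontinuation.

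Four stronger readings are tempting, and the documents do not support them:
- *The primary analysis becomes a per-protocol comparison.* That would need nearly all non-adherent children to be removed, which no section says.
- *The drug effect is necessarily inflated.* The direction depends on who is removed from which arm.
- *Power falls below 81%.* Dilution by non-adherence would be present equally if these children were kept. The effect size of 0.50 is already set below those of the two prior studies (0.87 and 1.75) and is not stated as an effect among adherers only.
- *Section 8.11.1 already guarantees retention.* Its sentence concerns treatment failures who may receive clinical treatment. Its reasoning extends to non-adherent children, but its wording does not.

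**Conclusion.** The conflict is real and avoidable. As written, section 4.8 can create missing outcomes through a choice made after randomization, and the plan does not say what happens to the AHI of those children. The promise that the primary analysis "will include all subjects randomized at Visit 1" cannot be kept for a child removed before Visit 2.

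The likely size at 3 months is small. Within the plan's own 5% dropout it is about 0.2/hr on an effect of 4.0/hr (roughly 5%), assuming that non-adherent NCS children get no benefit and all are removed. The bias could also run against NCS. The 12-month comparison is more exposed, because adherence is measured twice before its sleep study and the arms are smaller. No figure is put on it, since the documents give no rate of non-adherence or of removal.

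**What to change.** Reword section 4.8 so that non-adherence, a protocol deviation or an administrative reason does not end outcome follow-up. Such children are still asked to attend the scheduled Visit 2 sleep study, and the Visit 5 sleep study if re-randomized, whether or not they still take study drug. They are analysed as randomized.

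In section 4.8.1, say whether the visit applies to children discontinued by the investigator. State that an early-termination sleep study does not replace the scheduled one in the primary analysis and is used only in a sensitivity analysis.

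The safety-based withdrawals, including those for DXA and eye findings (sections 3.1.2, 3.1.3, 3.4.2 and 4.8), are for the sponsor. A rule that only withdrawal of consent ends follow-up would override them and is not proposed. Sections 4.8, 4.8.1, 6.3.2 and 8.11.1 need only be reconciled on whether outcome data are still collected after such withdrawals.

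The cost is protocol wording, some effort to keep non-adherent families in contact, and possibly a scheduled sleep study in addition to an early-termination one for a few children. No new type of procedure is needed. Some families will still decline, so the change reduces missing AHI but does not eliminate it.

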4.8.1 Early Termination Study Visit

Subjects who withdraw from the study will have all procedures enumerated for Visit 5 at the early termination visit.

